### 5.3.3 Occurrence of MAKE

Endpoints related to MAKE are as follows:

- Proportion of subjects experiencing either MAKE30, MAKE60, or MAKE90
- Proportion of subjects experiencing MAKE30
- Proportion of subjects experiencing MAKE60
- Proportion of subjects experiencing MAKE90

MAKE30 is defined for subjects with AKI incidence PostOp through Day 5 as follows

- Death (of all cause) and date of death < date of surgery + 30, or
- Need for dialysis and date of dialysis < date of surgery + 30, or
- $(\text{eGFRD}_{30} - \text{eGFR}_{\text{BL}}) / \text{eGFR}_{\text{BL}} \leq -0.25$  PostOp through Day 30

MAKE60 is defined for subjects with AKI incidence PostOp through Day 5 as follows

- Death (of all cause) and date of death < date of surgery + 60, or
- Need for dialysis and date of dialysis < date of surgery + 60, or
- $(\text{eGFRD}_{60} - \text{eGFR}_{\text{BL}}) / \text{eGFR}_{\text{BL}} \leq -0.25$  PostOp through Day 60

MAKE90 is defined for subjects with AKI incidence PostOp through Day 5 as follows

- Death (of all cause) and date of death < date of surgery + 90, or
- Need for dialysis and date of dialysis < date of surgery + 90, or
- $\text{eGFRD}_{90} - \text{eGFR}_{\text{BL}} / \text{eGFR}_{\text{BL}} \leq -0.25$  PostOp through Day 90

where  $\text{eGFR}_{\text{BL}}$  is eGFR at baseline (Day 1 PreOp),  $\text{eGFR}_{30}$ ,  $\text{eGFR}_{60}$ , and  $\text{eGFR}_{90}$  are eGFR on Days 30, 60, and 90, respectively. Note, eGFR (mL/min/1.73m^2) is calculated using 2009 CKD-EPI equation:

$$141 \times \min(S_{\text{Cr}}/\kappa, 1)^{\alpha} \times \max(S_{\text{Cr}}/\kappa, 1)^{-1.209} \times 0.993^{\text{Age}} \times 1.018 \text{ [if female]} \times 1.159 \text{ [if African American]}.$$

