9.3 Study Design

[figure not shown]
This is a Phase 2, multicenter, double-blind, randomized, placebo-controlled study to evaluate the effect of RBT-1 on preconditioning response biomarkers in subjects who are at risk for AKI following cardiac surgery. Eligible subjects will be randomized to receive a single dose of low-dose RBT-1 (45 mg SnPP/240 mg FeS), high-dose RBT-1 (90 mg SnPP/240 mg FeS), or placebo (normal saline) via IV infusion over a 120-minute period ≥ 24 but ≤ 48 hours prior to scheduled cardiac surgery.

All subjects will be assessed through Day 90 post-cardiac surgery. Subjects will be evaluated at Screening, 48 and/or 24 hours prior to surgery depending on the time of dosing, on Day 1 (day of surgery) and daily through Day 7 or Discharge if earlier, as well as on Days 30, 60, and 90, as described in the Event Schedule (see [Section 5](#)).

Assessments include biomarkers of preconditioning response and tubular injury, urine

output, incidence and severity of AKI, serum creatinine, days on ventilator, days in ICU, hospital length of stay, readmission rate, and safety (physical examination, clinical laboratory assessment, vital signs, concomitant medications, and adverse events). Evaluations for MAKE (death, need for dialysis, and change in kidney function) and safety will be performed through Day 90, as described in the Event Schedule (see Section 5).

The duration of the study will be approximately 90 days per subject. A schematic of the study design is presented below:

AKI = acute kidney injury; FeS = iron sucrose; h = hour; SnPP = stannous protoporphyrin

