## 2.2 Study Objectives

The overall objective is to evaluate the effect of RBT-1 on preconditioning response biomarkers in subjects undergoing CABG and/or cardiac valve surgery.

The primary objective is to evaluate the efficacy of RBT-1 in generating a preconditioning response as measured by a composite of plasma biomarkers (plasma heme oxygenase-1 [HO-1], ferritin, and interleukin-10 [IL-10]) from Baseline (pre-dose) through Day 1 PreOp.

The secondary objectives are to evaluate the efficacy of RBT-1 on the following:

- Change in renal tubular injury biomarkers post-cardiac surgery through Day 3
- Reduction in urine output (documented adverse event [AE] of sustained reduction in urine output, oliguria, or anuria) post-cardiac surgery through Day 5
- Incidence of AKI (defined as a  $\geq 1.5X$  baseline, i.e., a 50% increase from baseline in serum creatinine; documented AE of sustained reduction in urine output, oliguria, or anuria; or initiation of dialysis) post-cardiac surgery through Day 5

The exploratory objectives are to evaluate the following:

- Severity of AKI post-cardiac surgery through Day 7
- Mean increase in serum creatinine post-cardiac surgery through Day 7 or until Discharge if prior to Day 7
- Occurrence of MAKE – death, need for dialysis, and persistent renal dysfunction ( $\geq 25\%$  decrease in estimated glomerular filtration rate [eGFR]) – post-cardiac surgery through Day 30 (MAKE30) and Day 90 (MAKE90) post-cardiac surgery
- Proportion of subjects experiencing MAKE30
- Proportion of subjects experiencing MAKE90
- Days on ventilator
- Days in intensive care unit (ICU)
- Hospital length of stay
- Readmission rate
- Changes in biomarkers of RBT-1 activity and/or kidney function

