### 5.2.3 Incidence of AKI

The incidence of AKI post-cardiac surgery through Day 5 will be defined as:

- An absolute increase from baseline to  $\geq 1.5 \times$  Baseline at any time; or
- A documented AE of sustained reduction in urine output, oliguria, or anuria; or
- Initiation of dialysis

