## 5.3 Exploratory Efficacy Endpoints

### 5.3.1 Severity of AKI

Maximum severity of AKI post-cardiac surgery through Day 7 will be a categorical variable. It is defined as the maximum severity over Days 2 through 7 for subject with AKI incidence PostOp through Day 7 (replacing Day 5 with Day 7 in Section 5.2.3) as follows:

Stage 1      if  $\text{Creat}_{\text{Di}} - \text{Creat}_{\text{BL}} \geq 0.3 \text{ mg/dL}$ , or

	$1.5 * \text{Creat}_{\text{BL}} \leq \text{Creat}_{\text{Di}} < 2 * \text{Creat}_{\text{BL}}$ (i=2 to 7)
Stage 2	if $2 * \text{Creat}_{\text{BL}} \leq \text{Creat}_{\text{Di}} < 3 * \text{Creat}_{\text{BL}}$ (i=2 to 7)
Stage 3	if $\text{Creat}_{\text{Di}} - \text{Creat}_{\text{BL}} \geq 4$ mg/dL, or $3 * \text{Creat}_{\text{BL}} \leq \text{Creat}_{\text{Di}}$ (i=2 to 7), or need for dialysis and date of dialysis < date of surgery +6

where  $\text{Creat}_{\text{BL}}$  is creatinine at baseline (Day 1 PreOp),  $\text{Creat}_{\text{Di}}$  is creatinine on Day  $D_i$  (i.e., Days 2, ..., 7).

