## 7.5 Efficacy Analysis

Primary endpoint will be analysed using both the ITT and MITT populations. All other efficacy endpoints will be analyzed using the MITT population.

Surgery type and time on pump may be used as covariates in ANCOVA or MMRM, or as stratification factor in Cochran-Mantel-Haenszel (CMH)  $\chi^2$  test. When used as stratification factor, time on pump will be trichotomized by the approximate tertile ( $\leq 90$ ,  $>90$  to  $120$ ,  $>120$  minutes) of the distribution in the MITT population. Other variables (eg, AKI risk factor and investigator site) may also be considered as covariates or stratification factors. The decision for including/excluding these variables as covariates or stratification factors will be based on the blinded review prior to any unblinded analysis.

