#### **7.5.3.4 Occurrence of MAKE**

Proportions of subjects with (1) either MAKE30, MAKE60, or MAKE90, (2) MAKE30, (3) MAKE60, and (4) MAKE90 will be calculated and analyzed using the Fisher's exact test as described for the reduction in urine output.

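### SAP 5.3.3 counts death and dialysis as MAKE only in subjects with AKI by Day 5, and AKI stage and MAKE use a different baseline from the AKI endpoint they build on

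*SAP*

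**What the plan says.** **MAKE.** SAP 2.2 gives the components as "death, need for dialysis, and persistent renal dysfunction", the last being an eGFR fall of at least 25%. The protocol synopsis names the same components, and Protocol 9.3 says "Evaluations for MAKE (death, need for dialysis, and change in kidney function) and safety will be performed through Day 90". None of these makes AKI a condition.

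SAP 5.3.3 is the operational definition. It opens with "MAKE30 is defined for subjects with AKI incidence PostOp through Day 5 as follows", repeats that lead-in for MAKE60 and MAKE90, and places all three components under it. SAP 7.5.3.4 says "Proportions of subjects with (1) either MAKE30, MAKE60, or MAKE90, (2) MAKE30, (3) MAKE60, and (4) MAKE90 will be calculated" and plans no version without the condition. SAP 7.5 sets the population: "All other efficacy endpoints will be analyzed using the MITT population".

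**AKI.** Under SAP 5.2.3, AKI through Day 5 is creatinine of at least 1.5 times baseline, a urine-output adverse event, or "Initiation of dialysis".

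**Baseline.** SAP 4.1 defines baseline as the last value before study drug, usually Visit 1a, unless specified otherwise. SAP 5.2.3 specifies nothing else, so 4.1 applies to AKI incidence. SAP 5.3.2, 7.5.3.2 and 7.5.3.3 name Visit 1a, and Protocol 11.3 uses the pre-dose value for all endpoints. Two sections differ. In 5.3.1 the reference "is creatinine at baseline (Day 1 PreOp"), and in 5.3.3 it "is eGFR at baseline (Day 1 PreOp"). Both values are taken after dosing.

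**Dialysis windows.** Stage 3 in 5.3.1 needs dialysis earlier than surgery date + 6, for a severity measure that runs through Day 7. MAKE30 in 5.3.3 needs dialysis earlier than surgery date + 30. SAP 4.2 makes the day of surgery Day 1.

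**The concern.** MAKE is meant to capture hard renal outcomes and death. With AKI by Day 5 as a precondition, recorded MAKE partly re-measures early AKI. Protocol 6.4 hypothesises that RBT-1 reduces AKI, so the gate is itself a possible treatment effect. If the denominator is all MITT subjects, as 7.5 and Table 14.2-7.1 indicate, a drug that lowered AKI and nothing else would show lower MAKE with no change in deaths or late dialysis.

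The baseline choice is a second inconsistency within the same derivations. A subject enters the severity and MAKE definitions by comparison with the pre-dose creatinine and is then graded against a post-dose value. When the two differ, the subject can have AKI but no stage, or change MAKE status in either direction. No reason is given for the switch.

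**Working it through.** The plan states no event rate, power or sample size for MAKE or AKI stage, so there is no figure to reproduce. The definitions were applied as written.

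**1. Who the gate removes.** Dialysis started by Day 5 is itself AKI under 5.2.3 and still counts. What is lost is any death, and any dialysis first started after Day 5, in a subject without AKI by Day 5.

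Inputs: 126 subjects planned (protocol synopsis); AKI rate p, assumed 20–40%. Protocol 6.1 gives about 30% as background, not under the 5.2.3 definition. RR is the assumed ratio of the risk of death or late dialysis with AKI to that without, 1–4.

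- Subjects who can never be a MAKE case = 126 × (1 − p).
- Share of deaths and late dialysis uncounted = (1 − p) / [(1 − p) + p × RR].

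| p | Never a case | RR 1 | RR 2 | RR 4 |
|---|---|---|---|---|
| 0.2 | 100.8 | 80% | 67% | 50% |
| 0.3 | 88.2 | 70% | 54% | 37% |
| 0.4 | 75.6 | 60% | 43% | 27% |

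At an assumed risk of 2–5% by Day 90 there are 126 × 0.02 = 2.5 to 126 × 0.05 = 6.3 such events. Uncounted: from 2.52 × 0.273 = 0.7 to 6.3 × 0.80 = 5.0.

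**2. Spurious difference.** Assume AKI of 30% on placebo and 20% on active, and death or late dialysis of 5% in both arms, independent of AKI. Counted rates over all subjects are 0.30 × 5% = 1.5% and 0.20 × 5% = 1.0%, although the true rates are equal.

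**3. Baseline and MAKE.** The 2009 CKD-EPI equation is given in 5.3.3, with its constants in Appendix B. For creatinine above kappa, eGFR is proportional to creatinine to the power −1.209. If PreOp creatinine differs from Visit 1a by a fraction d, a 25% loss from PreOp equals a loss from Visit 1a of 1 − 0.75 × (1 + d)^−1.209:

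| d | −10% | −5% | +5% | +10% |
|---|---|---|---|---|
| Equivalent loss | 14.8% | 20.2% | 29.3% | 33.2% |

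Examples for a man aged 68, without the race term:

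| Creatinine, mg/dL (Visit 1a / PreOp / Day 30) | Loss from Visit 1a | Loss from PreOp |
|---|---|---|
| 1.00 / 1.05 / 1.30 | 27.2% (meets 25%) | 22.8% (does not) |
| 1.10 / 1.05 / 1.36 | 22.6% (does not) | 26.9% (meets 25%) |

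**4. Baseline and stage.** Take the most exposed case, a peak of exactly 1.5b, where b is the Visit 1a value. This is AKI. Stage 1 from PreOp fails on the 0.3 mg/dL rule when PreOp exceeds 1.5b − 0.3, a rise over Visit 1a of more than 50% − 0.3/b. It fails on the 1.5-fold rule whenever PreOp is above Visit 1a.

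| b, mg/dL | 0.7 | 0.8 | 1.0 | 1.2 |
|---|---|---|---|---|
| Rise needed for no stage | 7.1% | 12.5% | 20% | 25% |

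The gap therefore mainly affects subjects with low creatinine.

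**5. Windows.** Day 1 is the surgery date, so Day 7 is surgery + 6. Earlier than surgery + 6 excludes Day 7. Day 30 is surgery + 29, so earlier than surgery + 30 includes Day 30. The two rules treat their last day differently.

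**The case against.** **The endpoints are exploratory, and much ungated information is reported anyway.** True. Deaths appear in the safety tables and among the adverse events of interest, and eGFR change through Day 90 is analysed without the gate. Late dialysis has no named ungated summary, and no planned table gives MAKE as 2.2 describes it. Nor would MAKE deaths necessarily match safety deaths once ungated, because the MITT and Safety populations differ. That mismatch is not a reason for the change.

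**The SAP supersedes the protocol, which leaves detail to it.** This can settle the difference from the protocol. It cannot settle the conflict between SAP 2.2 and SAP 5.3.3.

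**The lead-in might restrict the denominator instead.** The wording allows it, but 7.5 and Table 14.2-7.1 point to all MITT subjects. On either reading, deaths without early AKI are lost. A restricted denominator would replace the spurious difference in step 2 of the working with a comparison of subjects selected after randomisation.

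**The size is assumed.** It is. The upper figure of 5.0 events needs 20% AKI, a 5% event risk and no association with AKI, all together, and MITT may be smaller than 126. The low end is under one event across three arms. The defect in the definition does not depend on these rates.

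**SAP 4.1 allows exceptions, and the last value before surgery is a defensible reference for surgical injury.** Both points stand. The fault is that one derivation uses two baselines without explanation. No bias in favour of either arm has been shown.

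**Conclusion.** The concern holds and should be corrected. SAP 5.3.3 excludes deaths and late dialysis in subjects without early AKI, contradicts the SAP's own objective, and makes MAKE depend on an outcome the drug may change. Under the stated assumptions about 27–80% of those events, or 0.7–5.0 events in 126 subjects, would go uncounted.

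The baseline mismatch is real. A 5% difference between the two creatinine values moves the 25% eGFR threshold to an effective 20–29% loss from Visit 1a, and a 10% difference moves it to 15–33%. The documents do not say how much the two values vary, so the number of subjects affected is unknown. The Stage 3 window loses one day of dialysis.

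A smaller point for clarification is that AKI qualifying only by a urine-output adverse event meets none of the 5.3.1 stages, and the SAP does not say how it is handled.

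The primary analysis and the sample size are not affected.

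**What to change.** - In SAP 5.3.3, count all-cause death and dialysis in every MITT subject, with all MITT subjects in the denominator. Do not apply the AKI condition to either component. If it is kept for the eGFR component, add a sensitivity analysis without it.
- Use the SAP 4.1 pre-dose baseline (Visit 1a) in 5.3.1 and 5.3.3.
- Change the Stage 3 dialysis window in 5.3.1 to earlier than surgery date + 7, so that it covers Day 7.
- State how AKI that qualifies only by a urine-output adverse event enters the stage analysis.

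The cost is SAP wording and derivation code. Visit 1a creatinine, dialysis and deaths are already collected.

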### 5.3.4 Hospitalization Parameters

Parameters related to hospitalization are as follows:

- Number of days on ventilator
- Number of days in intensive care unit (ICU)
- Hospital length of stay in days
- Readmission rate, defined as the proportion of subjects who are readmitted to a hospital following discharge from the initial hospitalization for CABG and/or cardiac valve surgery

### **5.3.5 Change in Biomarkers of RBT-1 Activity and/or Kidney Function**

The change in each exploratory biomarker will be computed for the intervals from baseline (Visit 1A) to Day 1 (Visit 2), Day 2 (Visit 3), and Day 3 (Visit 4).

## **6 SAFETY PARAMETERS**

Safety will be assessed through adverse events (AEs) and serious adverse events (SAEs), clinical laboratory parameters, physical examination, and vital signs.

### **6.1 Adverse Events**

Adverse Event means any untoward medical occurrence associated with the use of a drug in humans, whether or not considered drug related. An AE can be any unfavorable and unintended sign (e.g., an abnormal laboratory finding), symptom, or disease temporally associated with the use of a drug, without any judgment about causality.

All AEs will be recorded on the designated study eCRF for each subject beginning with the administration of investigational product and ending with the date of the end of study treatment follow-up (Day 90). AEs will be followed by the Investigator until event resolution, the subject is lost to follow-up, or the AE is otherwise explained or not considered clinically significant by the Investigator. AEs not resolved by Day 90 will be considered ongoing.

When reporting AEs, the Investigator will assess the relationship or association of study drug in causing or contributing to the adverse event as well as the intensity of the adverse event.

Treatment-emergent AEs (TEAEs) will be defined as any AE where the AE start date is on or after the infusion start date. AEs related to study treatment will be defined as any AE where the relationship to study treatment is considered as “possible” or “related”.

### **6.2 Serious Adverse Events**

An adverse event is considered “serious” if, in the view of either the Investigator or Sponsor, it results in any of the following outcomes:

- Death
- A life-threatening adverse event
- Inpatient hospitalization or prolongation of existing hospitalization

- A persistent or significant incapacity or substantial disruption of the ability to conduct normal life functions
- A congenital anomaly/birth defect
- Other medically important event

Important medical events that may not result in death, be life-threatening, or require hospitalization may be considered serious when, based upon appropriate medical judgment, they may jeopardize the subject and may require medical or surgical intervention to prevent one of the outcomes listed in this definition.

### **6.3 Select Adverse Events of Interest**

Following is a list of adverse events of interest by MedDRA preferred term (tentative):

- Atrial fibrillation
- Delirium
- Vasoplegia
- Bleeding
- Myocardial infraction
- Stroke
- Heart failure
- AKI (combined AKI, ARF, AE report of sustained urine reduction)
- Death

Additionally, photosensitivity AEs will be identified.

### **6.4 Laboratory Parameters**

Screening laboratory samples will be processed at a local laboratory. All other laboratory samples will be processed at a central laboratory. For subjects who will be administered study drug on the same day of Screening, blood and urine samples will need to be collected for central laboratory analysis in accordance with Visit 1a.

Serum chemistry and hematology will be measured at Screening (Visit 0), Visit 1a, Day 1 PreOp (Visit 2), and on Days 2 to 7 (or discharge, whichever is earlier; Visits 3-8), Day 30 (Visit 9), Day 60 (Visit 10), and Day 90 (Visit 11). Serum CysC will only be measured at Visit 1a and on Days 30 (Visit 9) and 90 (Visit 11).

Serum chemistry parameters include total protein, albumin, bicarbonate, blood urea nitrogen (BUN), serum creatinine, total bilirubin, alkaline phosphatase, glucose, sodium, potassium, phosphate, calcium, magnesium, gamma-glutamyl transferase (GGT), alanine aminotransferase (ALT), aspartate aminotransferase (AST), and CysC.

Hematology parameters include RBC, hemoglobin, hematocrit, MCV, MCH, MCHC, platelets, MPV, RDW and WBC.

Blood and urinary biomarkers will be collected at Visit 1a, 1b, 2 (PreOp, 1h PostOp, 12h PostOp), 3 (Day 2) and 4 (Day 3).

Blood biomarkers include preconditioning response biomarkers (plasma HO-1, ferritin, and IL-10) and other biomarkers of RBT-1 activity and kidney function.

Urinary biomarkers include tubular injury biomarkers (KIM-1, CysC, and NGAL) and other biomarkers of RBT-1 activity and kidney function, which include but are not limited to urine albumin to creatinine ratio (UACR), urine protein to creatinine ratio (UPCR), beta-2-microglobulin, osteopontin, calbindin, clusterin, and VEGF.

Blood and urine samples may be collected by remote phlebotomy, such as through a mobile phlebotomist or other blood collection center, for a visit conducted virtually on Day 7, 30, 60, or 90.

## 6.5 Other Safety Parameters

Physical examinations should be performed at Screening, prior to dosing, prior to cardiac surgery on Day 1, Day 7, Day 30, and Day 90. Symptom-directed physical examinations may be performed on Days 2 – 6. Symptom-directed physical examinations may also be performed on Days 7, 30, and 90 if those visits are conducted virtually.

Weight and body mass index will be collected at Screening and on Day 90.

Vital signs (blood pressure, pulse rate, body temperature) will be collected throughout the study at Screening (Visit 0), Visit 1a, Day 1 PreOp (Visit 2), and on Days 2 to 90 (Visit 3 to 11). During hospitalization, vital signs will be recorded once per day.

At each post-cardiac surgery visit, the Investigator/study staff will record whether the subject is in the ICU, on a ventilator, has been discharged from the hospital, or readmitted to the hospital.

## 7 STATISTICAL METHODOLOGY

### 7.1 Determination of Sample Size

There will be three treatment groups; the two active (high dose [HD] 90/240 and low dose [LD] 45/240) groups will be compared to the control group. Using gatekeeping procedure for multiple comparisons and assuming the primary endpoint log composite score derived from this study is comparable to the score derived from the REN-003 and REN-001A studies (HD: mean  $\pm$  SD 1.30 $\pm$ 0.56, LD: 1.07 $\pm$ 0.52, and placebo: 0.19 $\pm$ 0.19), a sample size of 10 subjects per group will provide >80% power for the between group comparisons with two-sided  $\alpha=0.05$  significance level.

Using the REN-003 Study “FDA Safety Summary-1 Updated Feb2020.docx” non-surgical healthy volunteer and CKD patient data mixture, the secondary endpoint log composite score is estimated as 0.41  $\pm$  0.51. Thus, with the sample size of 10, 20, and 30 subjects per group, the study will have 40%, 69%, and 86% power, respectively, to detect a between active group and placebo group difference in the mean log composite score of 0.4, or a between group ratio of 1.5 in the composite score.

## 7.2 General Statistical Considerations

Continuous variables will be summarized overall and by treatment group using descriptive statistics (e.g., N, mean, median, standard deviation [SD], Q1, Q3, minimum and maximum), while categorical variables will be summarized with number and proportion of subjects for each category.

In addition to the data summary and between group comparison, all data will be presented in the data listings with subject ID, treatment group, and other pertinent information.

For serum creatinine and eGFR, missing or aberrant central lab test results will be replaced by the local lab test results if available, or if not available, by linear interpolation by the two data points before and after the missing data point (not applicable for Day 7, Day 30, 60, and 90 tests). If Visit 1a is missing, and the corresponding local lab is not available, it will be imputed with the screening local lab result. Day 7 (Visit 8) lab test is collected on the nominal Day 7. If patients are discharged early, their discharge values from Days 4, 5, or 6 will be reported as Day 7 values. If Day 7 is missing, and the corresponding local lab result is not available, it will be imputed with the last value collected Day 3 through Day 6. All imputations will be documented and signed off prior to the database lock for analysis. Biomarker values below the limit of quantification (LLOQ) will be replaced by the LLOQ value divided by 2. Biomarker values above the limit of quantification (ULOQ) will be replaced by the ULOQ value.

Unless specified otherwise, all between group comparisons and confidence intervals will use 2-sided  $\alpha=0.05$  significance level.

Statistical analyses will be performed using SAS version 9.4 or higher.

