### 7.5.3.2 Mean increase from baseline in serum creatinine

Mean changes and % mean changes from baseline (defined as Visit 1a) to the mean of creatinine PostOp through Day 7 (or discharge if earlier) will be summarized by treatment group. The between active treatment and placebo difference in mean change and % mean change will be analyzed using ANCOVA with treatment as main effect and baseline as a covariate. LSM difference and the associated 95% CI will be presented.

Additionally, the CMH test stratified by the baseline creatinine in approximately tertile ( $\leq 0.9$ ,  $>0.9$  to  $1.2$ ,  $>1.2$  mg/dL) will be carried out as a sensitivity analysis.

Analysis of change and % change from baseline to each post-dose visit through Day 90 (i.e., Days 1, 2, 3, 4, 5, 6, 7, 30, 60, and 90) will be analyzed using the mixed effects model for repeated measures (MMRM), which includes treatment, visit, and treatment-by-visit interaction as factors, baseline as a covariate, and subject as repeated measure unit. The LSM and 95% CI will be presented for each treatment group at each time point. In the computation, the variance-covariance matrix will be assumed AR(1) structure and the denominator degrees-of-freedom will be estimated using the improved Kenward-Rodger method. LSM and 95% for the between active dose and placebo group difference will also be presented at each time point.

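### SAP 7.2 lets single-imputed creatinine and eGFR values into the exploratory MMRM and the secondary AKI endpoint, which overstates Day 7 information and can both remove and create AKI events

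*SAP*

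**What the plan says.** SAP 7.2 sets a chain of replacement rules for serum creatinine and eGFR:

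- First, "missing or aberrant central lab test results will be replaced by the local lab test results if available". The SAP does not define an aberrant result.
- With no local result, the value is filled "by linear interpolation by the two data points before and after the missing data point". This step is "not applicable for Day 7, Day 30, 60, and 90 tests".
- For patients discharged early, "their discharge values from Days 4, 5, or 6 will be reported as Day 7 values". The text does not say whether the value is moved or copied, or that a real Day 7 sample takes precedence.
- If Day 7 is still missing and has no local result, "it will be imputed with the last value collected Day 3 through Day 6".
- As a safeguard, "All imputations will be documented and signed off prior to the database lock for analysis".

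The rules stand under general considerations and exempt no analysis. The analyses they reach are:

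- **AKI through Day 5 (SAP 5.2.3, secondary):** creatinine at or above 1.5 times baseline at any time, or a urine-output adverse event, or dialysis.
- **MAKE30, MAKE60 and MAKE90 (SAP 5.3.3, exploratory):** defined only for subjects with AKI through Day 5.
- **MMRM (SAP 7.5.3.2, exploratory):** change at Days 1 to 7, 30, 60 and 90, with AR(1) covariance.

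On timing, SAP 7.2 places the Day 7 sample on the nominal day, while SAP Appendix A allows 3 days either side. Appendix A schedules Days 4 to 6 only for patients still in hospital. Protocol 9.7.5 allows the Day 7 visit to be held remotely.

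**The concern.** Two separate things are at stake.

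**The MMRM.** A likelihood-based repeated-measures model uses each subject's available visits and is valid under missing at random without filling. If a discharge value is entered as Day 7, the model treats it as a measured Day 7 value. Day 7 then appears better informed than it is. Who gets filled depends on when the patient left hospital, and length of stay is itself an outcome of this trial.

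**AKI.** The creatinine criterion turns on a single value crossing a threshold inside a five-day window. Replacing an observed value, or inserting one that was never measured, can change the yes/no result. Because MAKE requires AKI, a changed flag carries through: a death or dialysis that counts towards MAKE in a subject flagged as AKI does not count in a subject who is not.

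**Working it through.** The plan gives no sample size, power or error rate that depends on these rules, so there is no stated figure to reproduce. The check applies the rules to small cases and then sizes the Day 7 effect under stated assumptions. All cases use baseline 1.0 mg/dL, so the AKI threshold is 1.5. Interpolation is a + (b − a) × (t − t_a)/(t_b − t_a).

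**1. Event removed.** Day 2 is 1.2, Day 3 is observed at 1.6, Day 4 is 1.3. If Day 3 is called aberrant and there is no local result, it becomes (1.2 + 1.3)/2 = 1.25. The series reads 1.2, 1.25, 1.3, and the creatinine criterion is no longer met.

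**2. Event created.** Day 4 is 1.2, Day 5 is missing with no local result, Day 6 is 2.0. Day 5 becomes (1.2 + 2.0)/2 = 1.6. The subject has AKI through Day 5 with no qualifying sample by Day 5; a Day 6 value has been used to define it.

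**3. Discharge value moved.** Day 4 is 1.2, and the Day 5 discharge value of 1.6 is moved to Day 7. Day 5 is then empty or, if interpolated, 1.2 + 0.4 × 1/3 = 1.33. The Day 5 event is lost either way.

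**4. Discharge value copied.** A Day 4 discharge value of 1.35 stays on Day 4 and is copied to Day 7. It counts twice. If Days 5 and 6 are also treated as missing and interpolated, both become 1.35 and one sample fills four visits. On that reading it would also meet, alone, the sensitivity rule in SAP 7.5.2.3 of a 0.3 mg/dL rise on two consecutive measurements (1.35 − 1.0 = 0.35 on Days 4 and 5).

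**5. Day 7 information in the MMRM.** Input from the documents: 42 subjects per group (Protocol synopsis). Assumptions, none in the documents: AR(1) correlation ρ of 0.5 to 0.9, treated as known; a share f of 25% to 75% discharged on Day 4 or Day 6 with no Day 7 sample; Days 1 to 7 only.

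Let g be the days from discharge to Day 7 and r = ρ^(2g). Relative to a Day 7 filled for everyone:

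- squared standard-error ratio = (1 − r)/(1 − f) + r
- effective n per group = 42 / (that ratio)

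| ρ | f | Discharge day | r | Squared ratio | SE ratio | Effective n |
|---|---|---|---|---|---|---|
| 0.9 | 0.25 | 6 | 0.81 | 0.19/0.75 + 0.81 = 1.063 | 1.03 | 39.5 |
| 0.7 | 0.50 | 6 | 0.49 | 0.51/0.50 + 0.49 = 1.51 | 1.23 | 27.8 |
| 0.7 | 0.50 | 4 | 0.118 | 0.882/0.50 + 0.118 = 1.88 | 1.37 | 22.3 |
| 0.5 | 0.75 | 4 | 0.016 | 0.984/0.25 + 0.016 = 3.95 | 1.99 | 10.6 |

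The first and last rows are the extremes of the assumed range. The filled analysis claims 42 real values per group where the observed data carry the information of about 11 to 40. Days 30, 60 and 90 are left out; under AR(1) in visit order they would lend some information to Day 7 and narrow the gap.

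**The case against.** The case for the plan has real content.

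- **Local results come first.** Interpolation is only a fallback, so cases 1 and 2 need a missing local result. This stands.
- **Filling a truly missing value erases no observed peak.** If the Day 3 value in case 1 had never been measured, an observed-values analysis would also record no event. The loss comes only from replacing an observed value or moving it out of the window. This stands.
- **The discharge rule can be read as visit windowing.** Appendix A's window covers Days 4 to 10, so assigning a Day 4 to 6 sample to the Day 7 visit falls inside it. That is fair, but it conflicts with the nominal day in SAP 7.2 and leaves open what happens when a real Day 7 sample exists.
- **There is a safeguard.** Imputations are documented and signed off before lock. However, blinding is not stated for this step, whereas the SAP does state it for choosing populations (Section 3) and covariates (Section 7.5).
- **Scope is limited.** AKI has two limbs that do not use creatinine, mean creatinine already stops at discharge (SAP 5.3.2), and a copied Day 7 value changes neither the 1.5-times result through Day 5 nor the Day 2 to 7 maximum. All of this stands.

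A reader might also infer three stronger things that the documents do not support:

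- **That the rules can only remove AKI events.** Case 2 shows otherwise.
- **That one discharge sample always enters four times.** That needs both copying and interpolation of days after discharge. SAP 7.2 states neither, and Days 4 to 6 are not scheduled once the patient has left hospital. The count is one if moved and two if copied.
- **That values are replaced because they are high.** The SAP leaves the term undefined; it does not make size the trigger.

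**Conclusion.** The concern holds in a bounded form. SAP 7.2 prescribes single imputation where the MMRM does not need it, and the filled values are treated as measured. That the rules feed the AKI, MAKE and MMRM derivations is implied by their placement and the absence of any exemption; it is not written out.

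For the MMRM, Day 7 precision is overstated by an amount that depends on discharge timing. Under the assumptions shown, the observed-data standard error is 1.03 to 1.99 times the filled one. For AKI, individual classifications can go wrong in both directions, and MAKE follows.

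The size of any between-group bias cannot be computed, because the documents give no discharge-day, missing-sample or creatinine-decline rates. One might assume a fall of 0.1 to 0.3 mg/dL after early discharge and a 10 to 20 point difference in early discharge, giving 0.10 × 0.1 = 0.01 to 0.20 × 0.3 = 0.06 mg/dL at Day 7. Both inputs are invented, so this is not a finding about this trial.

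AKI incidence is secondary; the MMRM and MAKE are exploratory. The primary biomarker endpoint is untouched. The change is worth making because it is cheap and improves a stated rule.

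**What to change.** In SAP 7.2 and the sections that rely on it:

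1. Derive AKI from observed central or local values, without interpolation.
2. Fit the MMRM to observed central or local values, with no interpolation and no carry-forward or relabelling of earlier values to Day 7.
3. Replace a central value only when the laboratory flags the sample as invalid, with that judgement made blind to treatment.
4. Use a real Day 7 sample, remote or in person, whenever one exists, and reconcile the nominal Day 7 in SAP 7.2 with the 3-day window in Appendix A.
5. Keep the present rules as a sensitivity analysis, stating there whether a discharge value is moved or copied and whether days after discharge are interpolated.

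No new data are needed. The costs are fewer Day 5 to 7 values in the tables, wider Day 7 intervals, and reliance on missing at random. That assumption deserves a sentence of its own, because sampling on Days 4 to 6 depends on still being in hospital, and dropping the fill does not by itself remove the dependence on discharge timing.
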